5.4.2.2. For United States Sites

Plasma will be collected by apheresis from qualified donors who have consented to donate using the equipment and technologies already in operation at the New York Blood Center following standard operating procedures. Donors are eligible to donate every 7 days. This will permit collection of CCP from the same donor at weekly intervals.

Plasma collection using the TRIMA® Accel™ technology (Terumo BCT)

The TRIMA® Accel™ technology allows the automated collection of different blood components and contains programs for plasma collection only. Disposable sterile kits for plasma collection are available (kits with 3 or 4 plasma bags). Dependent on the donor characteristics (calculated blood volume), plasma volumes up to 750 mL can be collected. The procedure starts with the collection of a small volume of blood in a sampling bag; this blood will be used for regulatory analyzes at NYBC (transfusion transmitted disease testing). During collection, blood is mixed with ACD-A (anticoagulant citrate dextrose, solution A), plasma is separated from blood cells by centrifugation and collected in 2 or 3 bags (depending on the target volume that has been pre-defined) based on the estimated total blood volume of the donor whereas blood cells are returned to the donor.

Plasma collection using the Alyx® component collection system (Fresenius Kabi)

This automated system can be used to collect plasma only. Samples required for regulatory analyses are taken directly from the collected unit after plasma collection is completed. During collection, blood is mixed with ACD-A to avoid clotting and centrifuged in a single use, sterile centrifugation bowl to separate plasma from blood cells. When separation is completed, plasma is

automatically transferred to the collection bag and thereafter, blood cells are returned to the donor.

5.4.2.3. For Brazilian sites

Plasma collection using the MCS®+ technology (Haemonetics)

This automated system can be used to collect plasma. Samples required for regulatory analyses and antibody seropositivity determination are taken directly from the collected unit after plasma collection is completed. During collection, blood is mixed with anticoagulant (sodium citrate 4%) to avoid clotting and centrifuged in a single use, sterile centrifugation bowl to separate plasma from blood cells. When separation is completed, plasma is automatically transferred to the collection bag and thereafter, blood cells are returned to the donor. Depending on donor characteristics, plasma volumes up to 600 mL can be collected.

5.4.2.4. For the Israeli site

Plasma will be collected by apheresis from qualified donors who have consented to donate, using the equipment and technologies already in operation at Magen David Adom Nationa Blood Services following standard operating procedures.

Because apheresis collection allows for plasma only collection while blood cells are returned to the donor, donor are eligible to donate every 14 days (at minimum). This will permit the collection of CCP from the same donor at weekly intervals. SARS-CoV-2 antibody titers will be monitored at each donation to ensure the presence of sufficient amounts of antibody for the treatment of patients suffering from COVID-19.

Plasma collection using the TRIMA® Accel™ technology (Terumo BCT)

The TRIMA® Accel™ technology allows the automated collection of different blood components and contains programs for plasma collection only. Disposable sterile kits for plasma collection are available (kits with 3 or 4 plasma bags). Depending on the donor characteristics (calculated blood volume), plasma volumes up to 750 mL can be collected. The procedure starts with the collection of a small volume of blood in a sampling bag; this blood will be used for regulatory analyses at Magen David Adom National Blood Services (transfusion transmissible diseases) and to establish the anti-SARS-CoV-2 seropositivity. During collection, blood is mixed with ACD-A (anticoagulant citrate dextrose, solution A), plasma is separated from blood cells by centrifugation and collected in 2 or 3 bags (depending on the target volume that has been predefined) based on the estimated total blood volume of the donor whereas blood cells are returned to the donor.

Plasma collection using the PCS®2 technology (Haemonetics)

This automated system is used to collect plasma only. Samples required for regulatory analyses and antibody seropositivity determination are taken directly from the collected unit after plasma collection is completed. During collection, blood is mixed with anticoagulant (sodium citrate 4%)

to avoid clotting and centrifuged in a single use, sterile centrifugation bowl to separate plasma from blood cells. When separation is completed, plasma is automatically transferred to the collection bag and thereafter, blood cells are returned to the donor.

5.5. Packaging, Labeling and Storage

Labels bearing the ISBT 128 donation identification will be printed and placed on all collection bags and blood tubes before donation. After donation, plasma will be shipped to a component processing facility at Héma-Québec, Canadian Blood Services, or New York Blood Center and will be frozen at -18°C within 8-24 hours of collection. In Hemorio and in Magen David Adom National Blood Services the plasma will be collected at the same place where the component process facility is located. When results of regulatory analyses become available (this usually takes less than 48 hours) and the product can be released for transfusion, a new label will be applied on the plasma bag showing all product information including the ABO group. The plasma will also be labeled as "convalescent plasma" at Canadian, Brazilian, and Israeli sites and "apheresis plasma" at United States sites.

5.5.1. For Canadian Sites:

The sponsor shall ensure that the drug bears a label that sets out the following information in both official languages:

- (a) a statement indicating that the drug is an investigational drug to be used only by a qualified investigator;
- (b) the name, number or identifying mark of the drug;
- (c) the expiration date of the drug;
- (d) the recommended storage conditions for the drug;
- (e) the lot number of the drug;
- (f) the name and address of the sponsor;
- (g) the protocol code or identification.

A segregated storage area will be set up and used to keep CCP apart from the other plasma products. A product list will be kept up to date in order to know at all times the volume of CCP available for each ABO blood group. When requested for transfusion, the products will be shipped to the hospital through the regular transportation system for blood products or to pre-identified regional "hub" hospitals where inventory will be maintained. Large sites and those at a geographical distance of more than 200 km may be permitted to hold a stock of one 500 mL dose for each ABO blood group and smaller sites will only be shipped the investigation product once a patient has been randomized to the active treatment arm.

5.5.2. For United States Sites:

The sponsor shall ensure that the drug bears a label that sets out the following information in English:

- (a) A statement indicating that the drug is a new drug limited by federal (or United States) law for investigational use only;
- (b) The name, number or identifying mark of the drug;

- (c) The expiration date of the drug;
- (d) The recommended storage conditions of the drug;
- (e) The donor identification number

After collection, processing, and completion of donor regulatory analyses, the product will be shipped to the hospital blood bank for storage. A segregated storage area will be set up and used to keep the CCP apart from the other plasma products. A product list will be kept up to date in order to know at all times the number of units available and their corresponding blood volumes and ABO types.

5.5.3. For Brazilian sites:

The sponsor shall ensure that the drug bears a label that sets out the following information in both official languages:

- (a) a statement indicating that the drug is for research use and should only be used by a qualified investigator;
- (b) the name, number or identifying mark of the drug;
- (c) the expiration date of the drug;
- (d) the recommended storage conditions for the drug;
- (e) the donor identification number;
- (f) the name and address of the blood center;

A segregated storage area will be set up and used to keep CCP apart from the other plasma products. A product list will be kept up to date in order to know at all times the volume of CCP available for each ABO blood group. When requested for transfusion, the products will be shipped to the hospital through the regular transportation system for blood products (to hospitals located in Rio de Janeiro area) and by plane to hospital located in other states, where inventory will be kept. Sites at a geographical distance of more than 200 km may be permitted to hold a stock of three 500 mL doses for each ABO blood group.

5.5.4. For the Israeli site:

The sponsor shall ensure that the drug bears a label that sets out the following information in Hebrew:

- (a) The name, number or identifying mark of the drug;
- (b) The expiration date of the drug;
- (c) The recommended storage conditions of the drug;
- (d) The donor identification number

After collection, processing, and completion of donor regulatory analyses, the product will be shipped to the hospital blood bank for storage. A segregated storage area will be set up and used to keep the CCP apart from the other plasma products. A product list will be kept up to date in order to know at all times the number of units available and their corresponding blood volumes and ABO types.

5.6. Anti-SARS-CoV-2 seropositivity

There is currently no clinically validated method to characterize the therapeutic potency of COVID-19 convalescent plasma. Importantly, non-convalescent plasma selected from the general population based on titers of neutralizing antibodies did not show efficacy in the treatment of influenza in 3 large RCTs questioning reliance of such assay to predict efficacy^{45–47}. Because the validity of such assays to determine the therapeutic value of CCP constitutes an important clinical question, the neutralizing activity of plasma samples will be documented for all samples and correlated with treatment effect as an exploratory objective. These assays can be performed before or after the plasma has been released.

However, as a minimal requirement, anti-SARS-CoV-2 seropositivity must be demonstrated on donor sample prior to release of product. This can be done by ELISA or with a neutralizing assay. In the U.S sites, seropositivity may be assessed after transfusion of the product for a minority of donors. The majority of donors will be referred by the treating center to the donor center and prescreened for seropositivity prior to donation. However, if CCP units from the referred donors are unavailable, a general pool of CCP plasma can be used with seropositivity assessed from a tail segment following transfusion.

5.6.1. ELISA or Chemoluminescence

The ELISA or Chemoluminescence will specifically test for antibodies directed against the receptor binding domain (RBD) of SARS-CoV-2 glycoprotein S, which have been reported to correlated with plasma neutralizing activity (R^2 =0.96) ⁴⁸.

The American Association of Blood Banks (AABB) provides no guidance with regards to a specific titer cut-off value to qualify convalescent plasma as the optimal titer is currently unknown. The cut-off for seropositivity will be set as the mean value + 3 SD of the ELISA signal obtained with SARS-CoV-2 negative plasma (pool of plasma samples collected before 2020) at a 1:100 plasma dilution.

5.6.2. Functional assays

Functional neutralization assays can also be used as a criteria to confirm seropositivity. The most direct method involves adding the diluted plasma to a specific number of infectious particles (in this case SARS-CoV-2 virus), plating the virus, and measuring the number of plaques that can still be formed. This provides insights into the levels of neutralizing antibodies and for treating Covid-19. If used to qualify donation, a dilution of 1/160 will be used as threshold neutralizing titer will be used to confirm donor eligibility.

The antibody-dependent cell cytotoxicity assay, which measure Fc function of antibodies will also be performed on all plasma samples as per the study's exploratory objective but will not be used as a criteria to qualify donations.

5.7. Administration

The investigational product will be administered by a bedside nurse or other clinical team member that is qualified and licensed to administer blood products. Administration date and time, will be entered into the case report form (CRF). The one (500 mL) or two (250 mL) plasma units collected from one or two donors will be considered one treatment dose.

- a. The plasma will be administered at an infusion rate of no more than 150 mL/h and a standard test dose of 50 mL/hour for the 15 minutes or as per local procedures is mandatory.
- b. If an AE develops during infusion, the infusion will be stopped and can be restarted as per investigator's decision in consultation with the bedside physician.
 - i. Most reactions to plasma are relatively minor (urticaria or volume overload) and the infusion can generally be continued. Infusion can generally be continued in cases of itching or urticarial reactions after pausing the transfusion, administering antihistamines, and observing the patient for worsening.
- c. Severe allergic reactions such as, bronchospasm and hypotension, and will require discontinuation of the infusion.
- d. Transfusion of each unit must be completed within 4 hours of removal from storage. The complete study product (either 1 x 500 mL or 2 x 250 mL) must be infused within 24 hours of randomization.
- e. No medication or solution may be added to or infused through the same tubing simultaneously, unless the solution has been approved by Health Canada for this use (i.e. normal saline).
- f. Participants must be under direct or remote observation during the first 15 minutes. Vital signs should be assessed at 15 minutes, midway through the infusion and at the end of the infusion.

The maximum tolerated dose of AFP has not been determined. The most likely adverse effect from the transfusion would be hypervolemia which may be treated with diuretics in symptomatic patients by the bedside physician. Any over-dosage needs to be reported as per section 9.10.2.

5.8. Dose of CCP

The dose of CCP will be approximately 500 mL. This will be administered as be either 1 unit of 500 mL or 2 units of 250 mL of apheresis CCP.

5.9. Return and/or Destruction of Investigational Product

After the study treatment period has ended or as appropriate over the course of the study, disposition of unused and used plasma will occur following site procedures in the study protocol. In the context of the COVID-19 pandemic, this may include disposal of the used plasma in the biohazard disposal in the patient room. The final disposition of the product will be confirmed in the Laboratory Information System used by the hospital Blood Bank and provided to the investigator team to be kept in the investigational product log. These logs will be verified periodically by study monitors. Any site found to use a study product on a non-CONCOR-1 trial patient will be

immediately suspended to trial enrollment and the local REB/IRB and regulatory authorities will be notified.

At the completion of the study, there will be a final reconciliation of investigational product shipped, used, and remaining. This reconciliation will be documented. Any discrepancies noted will be investigated, resolved, and documented prior to return or destruction of unused investigational product. Documentation of investigational product destroyed on site will be retained in the study files.

5.10. Blinding and Breaking the Blind

This is an open-label trial.

5.11. Investigational Product Accountability

The site PI is responsible for study product distribution and disposition and has ultimate responsibility for study product accountability. The site PI may delegate to the participating site's blood bank responsibility for study product accountability.

The participating site's blood bank will be responsible for maintaining complete records and documentation of study product receipt, accountability, dispensation, storage conditions, and final disposition of the study product(s).

All study product(s), whether administered or not, must be documented on the appropriate study product accountability record or dispensing log. The sponsor's monitoring staff will verify the participating site's study product accountability records and dispensing logs per the site monitoring plan.

5.12. **Compliance**

CCP will be transfused in the clinical area by the patient's nurse or physician, with oversight from the study team (site PI and/or site RA) who will not enter the room, thereby ensuring compliance with the investigational product and good practices in the context of the COVID-19 pandemic.

5.13. Prior and Concomitant Medication

A concomitant medication is any treatment received by the subject concomitantly to any investigational medicinal products (IMPs) or during study participation.

Concomitant medications in a hospitalized population change daily and are difficult to collect and attribute to success and failure of therapy and impact on safety. Therefore, only selected concomitant medications will be recorded in this trial. The list of medications will be assessed only from 7 days prior to enrolment to Day 30 or discharge, whichever comes first, and will be detailed in the study operations manual.

6. STUDY OUTCOMES

6.1. Primary Outcome:

The primary outcome is a composite of intubation or death at Day 30.

6.2. Secondary Outcomes:

- Time to intubation or death
- Ventilator-free days
- In-hospital death by Day 90
- Time to in-hospital death
- Death by Day 30
- Length of stay in ICU
- Length of stay in hospital
- Need for ECMO
- Need for renal replacement therapy
- Myocarditis
- Patient-reported outcome at Day 30
- Incremental cost per quality-adjusted life year (QALY)
- CPP transfusion-associated AEs
- Grade 3 and 4 SAEs
- Cumulative incidence of Grade 3 and 4 SAEs (CTCAE)

7. DURATION OF FOLLOW-UP

Subjects will be followed daily until hospital discharge or death. Patients discharged from hospital before Day 30 will be contacted by telephone on Day 30 ± 3 days to ascertain any AEs, vital status (dead/ alive), hospital readmission and need for mechanical ventilation after discharge. Patients with a prolonged hospital admission will be censored for the outcome of in-hospital death at Day 90.

For patients who are pregnant or who become aware that they are pregnant between the period of randomization and Day 30, we will record their expected date of delivery and we will contact the patient after delivery to obtain information regarding any maternal or fetal adverse outcomes.

8. DATA COLLECTION AND SCHEDULE OF EVENTS

The local study coordinator will collect all study data and record the data in the CRF (electronic and/or paper) as per local study procedures and requirements for each site.

8.1. Data to be collected from the blood supplier

De-identified data on the plasma donor will be obtained from the blood suppliers. For Canadian and Brazilian sites, this data will include unit information (such as ABO group, volume, antibody titre) and donor information (such as age, sex, symptom onset, severity, treatment, date of resolution) and will be sent via secure file transfer in accordance with institutional protocols. For US sites and the Israeli site, the data will include ABO group, volume, antibody titre (retrospectively) and donor information (such as age, sex, symptom onset, date of resolution) and will be sent via secure file transfer in accordance with institutional protocols.

8.2. Subject Screening

At each participating site, there will be a process developed to immediately identify patients admitted to hospital with COVID-19. The local RA will then screen the patient for study eligibility, provide study details to the patient, and seek informed consent. Information from all patients approached for the study will be documented and logged using the screening study number including reasons for any exclusion. Once informed consent is obtained, a screening ABO blood group will be performed if one was not already performed during the patient's current hospital admission.

Once the ABO blood group testing has been performed, the remaining sample (discard) will be retained for future testing. Alternatively, an extra tube can be added to the routine blood draw for research.

8.3. Collection of daily hospital data

Baseline data will be collected on Day 1 (see Section 8.5).

During the index hospital admission, daily data will be collected until discharge or Day 30 from randomization, whichever comes first. For enrolled patients who are still in hospital beyond Day 30, the date of discharge or death will be recorded up until Day 90 at which point data collection will be censored. This information will be obtained by reviewing the medical chart, by telephone follow-up or, if feasible through, provincial/state or national databases.

If the patient has routine blood drawn for laboratory testing pre-randomization and between 24 hours and 5 days (sample closest to 48 hours will be selected in preference) post-randomization, the discard plasma/serum from that sample will be retrieved, aliquoted and frozen for future testing. Alternatively, an extra tube can be added to the routine blood draw for research.

A Schedule of Assessment Events is available below for reference.

Schedule of Assessment Events

			Follow up		
Visit	Screening	Baseline (D1)	D2 - D30 ⁽¹⁾ (or until discharge)	D30 ⁽²⁾ (if patients discharged)	D90
Time Window (days)				+/- 3	+/- 7 days
Informed Consent/Assent	Х				
Verify Eligibility Criteria	X				
Randomization		Х			
CCP Administration (3)		Х			
Demographics		Х			
Co-morbidities		Х			
COVID-19 History ⁽⁴⁾		Х			
Height and Weight		Х			
Vital Signs		Х			
SpO ₂		Х	Х		
FiO ₂		Х	X		
COVID treatments		Х	Х	Х	
Hospitalization Daily Assessment (5)		Х	X		
Results of blood tests (done as per		Х	X ⁽⁶⁾		
clinical need)					
EQ-5D-5L ⁽⁷⁾		Х		Х	
Vital Status (dead/ alive)			Х	Х	X
Adverse Event Review		Х	Х	Х	
Discharge status (8)				Х	
Mechanical Ventilation since discharge				Х	
Viral load, cytokines and anti-CoV-2 titers ⁽⁹⁾		Χ	Х		

⁽¹⁾ Only collected if still hospitalized

⁽²⁾ Phone call if subject is already discharged from the hospital

⁽³⁾ Only for subject randomized to the convalescent plasma treatment

⁽⁴⁾ Includes date of first symptoms; description of symptoms, and date of diagnostic test

⁽⁵⁾ Mechanical ventilation, ECMO, renal replacement therapy or myocarditis

⁽⁶⁾ Daily from Day 1-7, then Day 14 +/- 3 days

⁽⁷⁾ EQ-5D-5L to be collected on Day 1 after consent and prior to CCP administration and on Day 30 regardless of hospitalization status

⁽⁸⁾ Discharge or hospital status (admitted, home, local hospital, longterm care facility)

⁽⁹⁾ To be performed using frozen leftover sample or extra tube collected once at baseline and once during follow-up between 24h and 5 days post-randomization for both arms

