8.4. Baseline/Enrollment (Study Day 1)

Procedures/Assessments/Evaluations in this section will be completed after consent has been obtained, eligibility has been confirmed and the subject has been randomized. These do not need to be performed in the order listed below, but the administration of CCP must be the last procedure to be completed.

- 1- Demographics
- 2- Co-morbidities
- 3- Smoking status and pack-years for smokers
- 4- COVID-19 history (symptom onset, date of test, results of test)
- 5- Admission date
- 6- Oxygen saturation and PaO₂ (where available)
- 7- FiO2 and oxygen requirement (nasal prongs, oxygen masks, high-flow nasal cannula, noninvasive positive pressure ventilation)
- 8- Vital signs (temperature, pulse, respiratory rate, height, weight, and blood pressure)
- 9- Lab values
- 10- Patient-reported outcome instrument EQI-5D-5L 49
- 11- AEs since screening (if screening was not completed on the same day)
- 12- Concomitant medication review (if screening was not completed on the same day)
- 13- COVID-19 concomitant treatments including co-enrolment in another clinical trial
- 14- Administration of investigational product (according to study arm)

8.5. Collection of daily hospital data (Study Day 2 until discharge, death or Day 30 post randomization).

The following data and procedures will be collected daily.

- 1- Oxygen saturation and FiO₂
- 2- Mechanical ventilation requirement (via endotracheal tube or tracheostomy tube)
- 3- Admission to ICU
- 4- ECMO requirement
- 5- Renal replacement therapy requirement
- 6- Myocarditis
- 7- COVID-19 concomitant treatments
- 8- Blood product and blood transfusion information
- 9- AEs
- 10- Concomitant medication review
- 11- Chest x-ray and CT chest results
- 12- Discharge status (home, transfer to another facility, palliative discharge) collected from the hospital chart

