8.7. Discharge

- 1. Hospital / Discharge status (home/local hospital/longterm care facility)
- 2. Oxygen requirement
- 3. Need for mechanical ventilation
- 4. AEs

8.8. **Day 30**

- 1. Vital status (dead or alive)
- 2. Requirement for mechanical ventilation since discharge
- 3. Oxygen requirement
- 4. Hospital status (home/local hospital/longterm care facility)
- 5. Readmission to hospital (if discharged home/longterm care facility)
- 6. EQ-5D-5L
- 7. AEs

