2.2.6. Length of stay in intensive care unit

The number of days spent in the intensive care unit (ICU) over the 30-day period following randomization will be recorded. This total number of ICU days could be made up days from multiple admissions within the 30-day period from randomization if they are discharged and re-admitted a second time within this 30-day period. Patients will be contacted at Day 30 by telephone to determine whether there were any hospital admissions since discharge from the hospital they were in at the time of recruitment. Patients discharged from hospital will be assumed not to be in an ICU elsewhere, unless otherwise indicated.

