2.2.8. Need for Extra-Corporeal Membrane Oxygenation (ECMO)

This response will be a binary indicator indicating whether the patient required extra-corporeal membrane oxygenation during the 30-day period following randomization.

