4.3.4. Time to in-hospital death

The time to in-hospital death will be analyzed using a cause-specific Cox regression model to deal with the competing risks of discharge from the hospital in which the individual was randomized; for subjects hospitalized for more than 90 days their time of in-hospital death will be censored at 90 days. That is, individuals who did not die in the hospital they were admitted to at the time of randomization will have their follow-up censored at the time of discharge from this hospital. The regression coefficient and associated standard error from the cause-specific Cox regression model for death in the original hospital will be used to compute an estimate of the cause-specific hazard ratio along with a 95% confidence interval and a p-value. To accompany this analysis estimates of the cumulative incidence functions will be plotted for in-hospital death and discharge for each treatment group.

4.3.5. Death by Day 30

The probability of death between randomization and Day 30 will be estimated for each treatment group by the proportion of individuals randomized who died between randomization and Day 30. The test will be based on a 2-sided Wald test of the null hypothesis that the probability of death by Day 30 is the same among individuals receiving CCP or standard of care. The percent relative risk reduction will be estimated along with a 95% confidence interval and a p-value of the null hypothesis will be computed.

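### ECMO, renal replacement, myocarditis and ICU days run to Day 30 but have no matching data collection after transfer or discharge, and in-hospital death after transfer is handled in two ways

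*Protocol*

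**What the plan says.** **Collection window.** Protocol 8.3: "During the index hospital admission, daily data will be collected until discharge or Day 30 from randomization, whichever comes first". In the schedule of assessments, the Day 2 to Day 30 column carries the footnote "Only collected if still hospitalized". The daily assessment in that column is footnoted as "Mechanical ventilation, ECMO, renal replacement therapy or myocarditis"; it is marked at baseline and in that column, and not in the Day 30 column for discharged patients. Protocol 8.5 lists, among the daily items, "Discharge status (home, transfer to another facility, palliative discharge) collected from the hospital chart".

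**Day 30 contact.** For patients already discharged, Protocol 7 and 8.8 collect vital status, oxygen, hospital status, EQ-5D-5L, adverse events and "Requirement for mechanical ventilation since discharge". Protocol 8.8 also asks about readmission, but words that item for patients who went home or to long-term care.

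**Outcome windows.** SAP 2.2.8 asks whether the patient "required extra-corporeal membrane oxygenation during the 30-day period following randomization". SAP 2.2.9 and 2.2.10 set the same window for renal replacement and myocarditis. For ICU days, SAP 2.2.2 and 2.2.6 plan a Day 30 telephone question about ICU or hospital admissions since leaving the recruiting hospital, with this default: "Patients discharged from hospital will be assumed not to be in an ICU elsewhere, unless otherwise indicated".

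**In-hospital death.** SAP 2.2.3 counts a death in hospital within 90 days without saying which hospital. In the time-to-event analysis of SAP 4.3.4, "individuals who did not die in the hospital they were admitted to at the time of randomization will have their follow-up censored at" discharge from that hospital. Protocol 8.9 limits the Day 90 check to participants still hospitalized at Day 30 and does not say whether a second hospital counts.

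**The concern.** The period over which these outcomes are defined is longer than the period over which they are observed. SAP 4.3.8 to 4.3.10 estimate proportions among everyone randomized. Nothing in SAP 4.1 classes a transferred or discharged patient as having missing data, so complete-case analysis and multiple imputation do not come into play. A patient who starts dialysis or ECMO in a second hospital on a day inside the window enters the analysis as never having needed it.

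The gap matters most for patients moved to another acute-care hospital, because they may still be seriously ill. For them, discharge also ends length of stay (SAP 2.2.7) and censors time to in-hospital death. The cost analysis, which uses ICU, ventilator and ECMO use, inherits the gap. The trial is open-label, so it cannot simply be taken for granted that transfer, and therefore loss of events, is equal between arms.

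**Working it through.** **1. The plan's own figure.** Inputs from Protocol 12.1: 30% versus 22.5%, 400 versus 800 patients, two-sided 0.05. With pooled proportion 0.25:

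power = Φ{[d − 1.96·√(p̄(1−p̄)(1/400+1/800))] / √(p1(1−p1)/400 + p2(1−p2)/800)}

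= Φ{(0.075 − 0.0520)/0.0273} = 80.1%.

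The 1200 patients at 80% power reproduce. The point below does not touch this figure, because ventilation and vital status are asked after discharge.

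**2. One hypothetical patient, outcome by outcome.** The patient is transferred to another hospital on Day 4, has ECMO and dialysis in its ICU, and dies there on Day 25.

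| Outcome | Source after Day 4 | Result as written |
|---|---|---|
| Intubation or death at Day 30 | Day 30 vital status and ventilation | Event counted |
| Death by Day 30 | Day 30 vital status | Event counted |
| ECMO; renal replacement | None | No event |
| ICU days | SAP telephone question; no ICU item in Protocol 8.8, readmission item not applicable | Zero further days by default |
| In-hospital death by Day 90 (SAP 2.2.3) | Vital status, but no place-of-death item | Event by definition |
| Time to in-hospital death (SAP 4.3.4) | Not used | Censored at Day 4 |
| Length of stay (SAP 2.2.7) | Not used | Ends at Day 4 if transfer is a discharge |

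Myocarditis first diagnosed in the second hospital is lost in the same way as ECMO. Had the patient died in the second hospital between Day 31 and Day 90, SAP 2.2.3 would still count the death, but whether anyone looks for it depends on how Protocol 8.9 is read.

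**3. What lost events would do.** The documents give no transfer rate and no expected rate for ECMO or renal replacement. Everything here is assumed: control rate r of 2%, 5% or 10%, true relative risk 0.75, and a share f of events missed equally in both arms.

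Expected events = 400·r·(1−f) + 800·0.75·r·(1−f) = 1000·r·(1−f). Power uses the formula in step 1.

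| r | Events, f = 0 | Events, f = 0.3 | Power, f = 0 | Power, f = 0.3 |
|---|---|---|---|---|
| 10% | 100 | 70 | 32% | 24% |
| 5% | 50 | 35 | 19% | 14% |
| 2% | 20 | 14 | 10% | 9% |

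For uncommon events the standard error of the log relative risk grows by about 1/√(1−f), which is 1/√0.7 = 1.20 at f = 0.3. The relative risk itself is unchanged.

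With unequal loss, apparent RR = true RR × (1 − share missed in CCP)/(1 − share missed in control). Missing 10% in CCP and 20% in control gives 0.90/0.80 = 1.125. A true 1.00 then appears as 1.13, and a true 0.75 as 0.84.

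**The case against.** **Deaths.** A reader might infer that deaths over 30 or 90 days are lost in general, and might size this by multiplying 1200 by an assumed transfer share and an assumed fatality. The documents do not support that. Vital status at Day 30 is collected for every discharged patient, so such deaths count in the primary outcome and in Death by Day 30. SAP 2.2.3 is not restricted to the original hospital. The censoring is confined to time to in-hospital death; what remains beyond that is an inconsistency between SAP sections and an unclear Day 90 rule.

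**Upward transfer.** It is tempting to say that the sickest patients leave observation because they deteriorated. Protocol 4.7 does include community hospitals, but no section gives the direction or frequency of transfer. The only hospital destination named, a local hospital, fits step-down at least as well.

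**ICU days.** The SAP does plan a telephone question, and its default applies only when nothing else is known. That stands. But Protocol 8.8, which defines what is recorded, has no item to receive the answer.

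**Other sources.** Adverse events of grade 3 or higher are collected to Day 30, and Protocol 8.3 mentions telephone follow-up and databases. Severe renal failure or myocarditis could surface in the adverse event review. Still, that review is not a defined source for ECMO, renal replacement or ICU days, and Protocol 9.2 excludes from serious events those already captured as outcomes. The databases are conditional on feasibility, and the sentence they support concerns dates of discharge or death beyond Day 30.

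**Estimand.** Death in the original hospital, with leaving it as the competing event, is a deliberate specification in SAP 4.3.4, so changing it is partly a matter of preference. Leaving it at odds with SAP 2.2.3 is not.

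**Power.** Under the assumed rates the ECMO and renal replacement comparisons are weak even with complete data. That limits what lost precision costs, but does not excuse a possible bias.

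**Conclusion.** The point holds for ECMO, renal replacement and myocarditis: all three are defined to Day 30, and no form field records them after transfer or discharge. It holds in part for ICU days, where the SAP foresees a question that the protocol's form does not carry and the readmission item leaves out patients transferred to another hospital. For death it is limited to an inconsistency: SAP 2.2.3 against SAP 4.3.4, with Protocol 8.9 silent on second hospitals.

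The primary outcome, its sample size and Death by Day 30 are unaffected. The size is unknown, because the documents give neither the rate nor the direction of transfer, and the figures above rest on assumed rates. Equal loss lowers precision and understates event proportions in both arms. Bias in the relative risk requires unequal loss, for which the documents offer no evidence either way. Several named secondary outcomes cannot be measured as defined, and the repair is cheap enough to make regardless of size.

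**What to change.** 1. Add ECMO, renal replacement, myocarditis and ICU dates since discharge or transfer to the Day 30 form in Protocol 8.8 and to the schedule. For transferred patients, complete them from the receiving hospital's record, and extend the readmission item to these patients.
2. Do not apply the no-ICU default of SAP 2.2.6 to patients transferred to another acute-care hospital.
3. Reconcile SAP 2.2.3, 2.2.4, 2.2.7 and 4.3.4 with Protocol 8.9. Treat direct transfer to another acute-care hospital as a continuation of the hospitalization, so that it is neither a discharge nor a censoring event, and apply the Day 90 check to these patients.

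The cost is a few fields on an existing form, a record request for transferred patients only, and SAP wording. No new visit is needed.
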